9. STUDY COURSE

Following the meeting with CNEDIMTS (HAS), three observation periods were defined with the following products:

- D1 to D5: intensive hospital treatment performed by the night and day wearing of the circaid® compression system versus the night and day wearing of short stretching tapes.
- B. DD (Day of discharge from the hospital) to DD +30: ambulatory initial maintenance phase carried out by the wearing of a compression sleeve on the day associated with the nighttime compression system circaid® versus wearing a compression sleeve on the day associated with a possible treatment at night, as recommended by HAS.
- C. DD + 31 to DD + 90: ambulatory maintenance phase carried out by the wearing of a compression sleeve on the day associated with the nighttime circaid® compression system versus the wearing of a compression sleeve on the day associated with possible treatment at night.

Study design:

The study therefore includes four medical follow-up visits on day 0 (D0), day 5 (D5) (+/- 1 day), day of discharge (DD) + 30 days (+/- 5 days) and DD + 90 days (+/- 10 days), followed by self-questionnaire during the maintenance phase between DD and DD + 90, DD designating the day of discharge from the hospital at the end of the intensive reduction phase.

At D0, the doctor:

- collects the informed written consent of the patient after having duly informed her;
- collects its socio-demographic characteristics: age, occupation;
- collects the characteristics of its lymphedema: origin, date of onset, stage of edema according to the classification of the international society of lymphology, laterality of edema, volume of the arm with lymphedema, and volume of lymphedema compared to contralateral arm;

- collects the quality of life measured by the Lymph IFC specific questionnaire;
- implements decongestive treatment with the product defined by randomization.

At D5 (+/- 1 day), the doctor:

- collects the characteristics of lymphedema: stage of edema according to the classification of the international society of lymphology, volume of the arm with lymphedema, and volume of lymphedema compared to the contralateral arm;
- completes the PGII and CGII;
- records patient satisfaction in terms of efficiency and comfort of wearing measured on Likert scales in 5 classes;
- collects the occurrence of adverse events and their imputability to the products under study according to the materiovigilance;

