13.1. SAMPLE SIZE

The sample size is based on the assumption that at the end of the maintenance period, 3 out of 4 patients will have at least a 20% decrease in the volume of their lymphedema in the circaid® group versus 1 in 2 in the control group. At risk alpha = 0.05, in a two-sided Chi2 test with a power of 80%, the calculation performed with Nquery (see table below) shows that the number of patients required to highlight this difference is 58 patients per group. This number is increased by 15% to account for patients lost to follow-up or unusable records, i.e. 68 per group. These patients will be recruited by 5 centers on the basis of 28 patients per center. Two group χ^2 test of equal proportions (odds ratio = 1) (equal n's)

Test significance level, α	0,050
1 or 2 sided test?	2
Group 1 proportion, π_1	0,250
Group 2 proportion, π_2	0,500
Odds ratio, $\psi = \pi_2 (1 - \pi_1) / [\pi_1 (1 - \pi_2)]$	3,000
Power (%)	80
n per group	58

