13.4. STATISTICAL METHODS

13.4.1. Description of the population and comparability of groups at inclusion

The sociodemographic characteristics and the characteristics of their lymphedema (origin, date of onset, stage of edema according to the classification of the international society of lymphology, laterality of the edema, volume of the arm with lymphedema, and volume of lymphedema compared to contralateral arm) will be compared between groups by Chi2 tests for qualitative variables and by Student's t-tests for quantitative variables, or their non-parametric equivalents if the characteristics of distributions require it.

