13.4.2. Study of the main objective

The frequency of patients whose lymphedema volume reduction is at least 20% of the initial volume is described by numbers, frequencies, 95% confidence intervals and compared between groups by a Chi2 test at DD + 30.

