13.4.3. Studies of secondary objectives

- The evolution of the volume of lymphedema will be compared between the groups by repeated-time analysis of variance with two time factors and treatment with interaction on D5, DD + 30 and DD + 90.
- The frequency of patients whose lymphedema volume reduction is at least of 20% of the initial volume is described by numbers, frequencies, 95% confidence intervals and compared between groups by a Chi2 test at D5 and DD + 90.
- The percentage of patients for whom 70% of the initial benefit of the reduction of lymphedema obtained on day 5 is kept at DD + 90 at the end of the maintenance phase is described by number, frequency, 95% confidence interval and compared between groups by a Chi2 test at DD + 90.
- The improvement of the discomfort will be described through the CGII and the PGII (Patient Global Improvement Impression) by numbers, percentages and 95% confidence intervals and compared between groups by Wilcoxon rank tests. The evolutions within each group will be compared by Wilcoxon tests on repeated series.
- The improvement of the quality of life will be described through the IFC-specific Lymph Questionnaire by means of means, standard deviations and 95% confidence intervals and compared between the groups by a two-factor repeated time analysis of variance with interaction measurement. A Student's t-test will compare their variations between the two groups. The evolutions within each group will be compared by t-tests on repeated series.
- Their compliance with the Morisky score, the satisfaction of the patients in terms of efficiency and wearing comfort, their opinion on the ease of use of the product (need of a third person, applications of pressure, continuation of his use, advice to third parties, comparison with possible previous treatments, ease of use) will be compared between groups by Chi2 test or by a Fisher test if the characteristics of the distributions require it.
- The frequency and nature of adverse events will be described in terms of numbers and frequencies and compared between groups by Chi2 tests or Fisher tests if required by distribution conditions.
- The evolution of the quality of life of the patients will be described by numbers, percentages and 95% confidence interval and compared between groups by Wilcoxon rank tests. The evolutions within each group will be compared by Wilcoxon tests on repeated series.

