- The frequency of those who use nurses or caregivers will be described by numbers, percentages, and 95% confidence intervals and will be compared between groups by Chi2 tests or Fisher tests if the characteristics of the distributions required it. The average number of nurse visits and its standard deviation will be calculated and compared between groups by Student's t tests. Its economic impact will be quantified by mean and standard deviation and compared by Student t tests on repeated series.
- The sociodemographic and clinical factors of patients likely to influence their adhesion, their satisfaction and the maintenance of the effect on lymphedema will be studied by logistic regression analyzes in order to identify those having a significant action after adjustments on the socio-demographic and clinics characteristic of the patients.

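### The exploratory logistic regressions for adherence, satisfaction and maintained effect do not list randomised arm, which modestly weakens them and hides whether a factor acts under both regimens

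*Combined protocol and SAP*

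**What the plan says.** Protocol section 13.4.3 ends with a bullet on determinants of adherence, satisfaction and lasting benefit. The candidates are patient-level factors, and the stated method is "logistic regression analyzes in order to identify those having a significant action after adjustments on the socio-demographic and clinics characteristic of the patients". That is the whole specification. It names no arm term, no arm-by-factor term and no separate fit by arm.

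Section 13.4.1 shows what the plan counts as patient characteristics: "The sociodemographic characteristics and the characteristics of their lymphedema (origin, date of onset, stage of edema", followed by laterality and the volumes. Arm is not among them, and the list in section 8.2 does not include it either.

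Elsewhere the plan names treatment when it is meant to be in a model. The volume analysis in section 13.4.3 is a "repeated-time analysis of variance with two time factors and treatment with interaction on D5, DD + 30 and DD + 90", and most of the other secondary outcomes are explicitly compared between groups.

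The regimens that patients adhere to and rate differ by arm. For the later maintenance phase, section 9 contrasts "the nighttime circaid® compression system versus the wearing of a compression sleeve on the day associated with possible treatment at night".

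Section 13.2 defers details to a later analysis plan to be built mainly on section 13. That later plan is not in the documents.

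**The concern.** Adherence and satisfaction refer to whatever the patient was given. In one arm that is a night device plus a day sleeve; in the other it is a day sleeve with night treatment only as an option. A model of these ratings without arm averages over two regimens.

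This has two consequences. First, in logistic regression, leaving out a variable that predicts the outcome pulls the other odds ratios towards 1 and costs power, even when that variable is independent of them. Second, a single pooled odds ratio per factor cannot tell the reader whether the factor matters with the device, with the control regimen, or with both. That distinction matters if the results are used to describe which patients do well on the device.

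**Working it through.** **The plan's own figure.** The documents size only the primary endpoint. Section 13.1 assumes 3 in 4 responders with circaid "versus 1 in 2 in the control group", two-sided alpha 0.05 and 80% power. With mean proportion 0.625:

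n = [1.960 × √(2 × 0.625 × 0.375) + 0.842 × √(0.75 × 0.25 + 0.50 × 0.50)]² / 0.25² = (1.342 + 0.557)² / 0.0625 = 57.7, so 58 per group, as stated. The odds ratio is (0.75/0.25)/(0.50/0.50) = 3.

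This odds ratio belongs to the ≥20% volume reduction. The documents give no arm effect for adherence, satisfaction or maintenance, so 3 is borrowed below and 5 is a further assumption. All runs use one binary factor with 50% prevalence and 58 per arm, with the outcome centred at 50% in control.

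**Attenuation, by hand.** Take a factor with odds ratio 2.5 in both arms (log 0.916).

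- Arm odds ratio 3: outcome rates with and without the factor are 0.613 and 0.387 in control, 0.826 and 0.655 with circaid. Pooled, they are 0.719 and 0.521. Pooled odds ratio = (0.719/0.281)/(0.521/0.479) = 2.35, log 0.856, which is 7% smaller.
- Arm odds ratio 5: circaid rates are 0.888 and 0.760; pooled rates 0.750 and 0.574; pooled odds ratio 2.23, log 0.803, which is 12% smaller.

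**Simulation, arm omitted v arm included.**

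| Scenario | Estimate | Factor significant at 0.05 |
|---|---|---|
| Factor OR 2.5, arm OR 3 | log-OR 0.88 v 0.95 | 60% v 62% |
| Factor OR 2.5, arm OR 5 | log-OR 0.85 v 0.98 | 54% v 59% |
| Factor OR 3, arm OR 3 | OR 2.84 v 3.09 | 75.0% v 77.5% |
| No factor effect, arm OR 3 | OR 1.01 v 1.02 | 4.7% v 4.4% |

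A repeat of the second row gave 50% v 56%. The loss is therefore about 2 to 3 points at an arm odds ratio of 3 and about 5 to 6 at 5. Type I error is not affected.

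**Factors that differ by arm (arm OR 3).**

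| True factor OR, control / circaid | Pooled OR, arm omitted | Flagged, arm omitted | Flagged, arm as main effect | Interaction test significant |
|---|---|---|---|---|
| 4 / 1 | 2.06 | 44% | 48% | 38% |
| 1 / 4 | 1.70 | 28% | 30% | 36% |
| 3 / ⅓ | 1.16 | 6% | 6% | 72% |

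The pooled odds ratio describes neither arm, and an arm main effect does not change that. Only an interaction term or by-arm estimates can. For a one-arm odds ratio near 3.5 (35% v 65% in control: (0.65/0.35)² = 3.45), a further run gave 32% interaction power. One-arm effects of this size therefore have about 30 to 40% power.

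**Multiplicity.** Section 8.2 lists eight baseline items: age, occupation, origin, date of onset, stage, laterality and two volumes. Eight independent null interaction tests at 0.05 give 1 − 0.95⁸ = 34% chance of at least one false positive. A simulated joint model with eight null binary factors and their arm interactions at 58 per arm gave 41%.

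**The case against.** The strongest reply is that one sentence in a protocol does not forbid an arm term, and section 13.2 leaves the procedures to a later plan. That is true, but the sentence does state an adjustment set and arm is not in it. If the later plan follows it, the omission carries over.

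It is also fair that section 13.4.3 already compares the adherence score, satisfaction and 70% retention of the D5 benefit between groups, so the arm effect on these outcomes is not lost. These regressions are secondary and exploratory. The attenuation is partly a matter of definition, because an odds ratio averaged over arms and one within arms are different quantities.

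Three stronger readings are tempting and do not stand.

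- A reader might infer that omitting arm biases the factors or produces false findings. Randomisation keeps baseline factors independent of arm apart from chance, and the false-positive rate stays near 5%.
- A reader might infer that omitting arm is why a one-arm factor gets reported as general. It is not: adding arm as a main effect slightly raises the flagging rate (44% to 48%). What is missing there is an interaction or by-arm estimate.
- A reader might infer that the primary comparison, "compared between groups by a Chi2 test at DD + 30", should have used these same factors and is defective without them. The bullet concerns maintenance of the effect, not the ≥20% response at DD + 30. The unadjusted test is valid and matches the sample-size method.

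**Conclusion.** The point holds in a limited form. The stated adjustment set omits randomised arm in models of outcomes that depend on the regimen received. The cost is modest: factor log-odds ratios about 7% smaller and 2 to 3 points of power if the arm odds ratio is 3, or about 12 to 13% smaller and 5 to 6 points if it is 5. Both arm effects are assumed, as are the single binary factor and the 50% control rate. The other cost is interpretive: a pooled result does not show whether a factor acts under both regimens. Validity of the factor tests, the primary Chi2 and the 58 per group are untouched.

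**What to change.** In the detailed analysis plan, add randomised arm as a fixed term in every logistic model of this bullet. Name in advance the few factors that will be interpreted. For those, report by-arm odds ratios with 95% confidence intervals or one arm-by-factor term each, labelled exploratory. State that power is low and that several interactions increase the chance of a false one; do not fit an interaction for every listed factor.

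The cost is one or two lines and one model parameter for arm. No new data are needed.

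Optionally, and as a separate matter, the plan could add a supportive covariate-adjusted arm effect on the DD + 30 response, with the Chi2 kept as the primary test. One or two pre-specified baseline covariates would suffice, for example lymphedema stage and baseline lymphedema volume. Using all listed factors is unwise at this size: with eight covariates at 58 per arm, the likelihood-ratio test had a simulated type I error near 6.4%, against about 4.7% for the Chi2.

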13.4.4. Intermediate analysis

Considering that the study is an open label study, an interim analysis may be conducted during the study when at least 50% of the initial enrollment has completed the study.

13.4.5. Analysis software

Data record will be done on capture system and the analyzes will be conducted using the SAS software version 9.4. The significance level is set to $\alpha = 0.05$.

14. REGULATORY OBLIGATIONS AND ADMINISTRATIVE PROCEDURES

In accordance with the principles of the Declaration of Helsinki (1964), reviewed in Tokyo (1975), Venice (1983), Hong Kong (1989), Somerset West (1996) and Edinburgh (2000), this trial should be conducted according to the rules of Good Clinical Practices, and according to the procedures applicable to biomedical research defined by the European directive 2001/20 / EC transposed by the decree n ° 2005-477 of April 26, 2006. This can moreover include an audit on site, by the sponsor, the Scientific Committee and / or an inspection by representatives of the health authorities, at any time. The investigator must accept the control of the source documents of the trial by the monitor, the representative of the health authorities, the representative of the sponsor and / or the scientific committee.

14.2. COMMITTEE FOR THE PROTECTION OF PERSONS (ETHIC COMMITTEE)

This protocol, the patient information form and the Patient Consent Form have been submitted to the "IDF 11" CPP.

Any amendment to the protocol must be reported to the CPP "IDF 11", and its favorable opinion will have to be obtained if the amendment is likely to significantly modify the safety conditions of the patients participating to the research.

14.3. PATIENT INFORMATION AND INFORMED WRITTEN CONSENT

In accordance with the European Directive 2001/20 / EC transposed by Decree No. 2005-477 of 26 April 2006, the patient must give her free and informed consent.

14.3.1. Patient information

Each patient meeting the selection criteria must be informed by the investigator of the purpose of the research, its methodology and duration, foreseeable constraints and risks, including if the research is terminated before completion, as well as the benefits he is entitled to expect from his participation.

The main points of information provided to the patient must appear on the information document that the investigator gives to the patient before the start of the trial.

The patient must know:

- she may refuse to participate in the research;
- that the inclusion visit and the follow-up visits are borne by the study sponsor and that she will not have to bear any additional direct or indirect financial burden due to its participation in the trial.

The investigator must answer any additional questions from the patient on the trial at the time of selection and throughout the duration of the research.

At her request, the patient will be informed by the investigator of the results of the trial in which she has participated.

14.3.2. Consent of the patient

Prior to its inclusion in the trial, the written, free, express, informed consent of the patient must be collected (European Directive 2001/20 / EC transposed by Decree No. 2005-477 of 26 April 2006) in a triplicate form.

The original is returned to the patient, a copy is kept by the investigator and the third copy is placed in a sealed envelope containing only the code of the test, the name of the investigator, the number of written consents that it contains and the date. This envelope is for the Medical Director of CEN Biotech who keeps it under his responsibility.

14.4. INFORMATION RETENTION, ARCHIVING

According to European regulations, all correspondence on the patients, ie the source documents, the observation books, the CPP's opinion and the correspondence relating to the trial, must be filed and kept in the archiving file for 15 years by the investigator.

14.5. DECLARATION TO THE CNIL

Patient notebooks are identified by the patient number, the first two letters of the name, and the first letter of the first name. In these circumstances, the trial falls under the simplified procedure related to clinical research. This procedure will be followed up before the beginning of the test. Patients participating in the trial will be informed of the indirect nature of the data collected on them in the trial newsletter, and will consent in writing to the trial consent form. They will also be informed that they have a right of information concerning them which will be exercised with CEN Gestion.

14.6. DECLARATION TO ANSM

This protocol, in accordance with the French law, is the subject of a declaration to the ANSM.

14.7. INSURANCE CERTIFICATE

The conduct of this trial is covered by an insurance policy contracted with HDI Global SE under the number 01005344514058 170036. A copy of the insurance certificate will be given to the investigator and kept in the investigator file. This document is presented in Annex 2 §16.2 of the protocol.

14.9. DISPENSATION OF PRODUCTS

medi France entrusts the investigating center with the mission of dispensing the study products, respecting the order of attribution of the products. Each patient will be allocated a batch of product consisting of all materials required for the study.

14.10. RETURN OF PRODUCTS

The circaid® devices used will be examined and recovered upon return to the final visit. Patients wishing to continue wearing them will be able to benefit from a new free delivery.

14.11. CONDITIONS OF PUBLICATION

The documents provided by medi France to the investigator, as well as the notebooks that he completes and the results are the property of medi France and their communication falls within the specific rules relating to studies defined by Article R 5121-13 of the Public Health Code.

The study may be published or communicated subject to the prior written consent of the sponsor, the coordinator and the principal investigator.

At the end of the trial, the patients will be able to have their overall results communicated on request to the investigator.

14.12. DATA SOURCES - ARCHIVING DOCUMENTS

The source documents, the observation books, the original consent forms, the signed protocol and all documents related to this trial must be legally retained by the investigator for a minimum of 15 years from the trial report. Archiving will be done in a closed room provided for this purpose.

The promoter organizes the storage of the test documentation in appropriate premises for at least the product's lifetime (European Directive 91/507 / EEC):

- protocol with annexes, amendments;
- notebooks with accompanying documents;
- follow-up document of the clinical study;
- all administrative documents and correspondence related to the study;
- statistical analysis report and study report (product life + 5 years);
- non-rewritable media copy of the "frozen" database of clinical data.

14.13. STOPPING OF THE STUDY

14.13.1. Study discontinuation by the sponsor

The sponsor may stop the study at any time for the following reasons:

- inability of the investigator to include patients according to schedule;
- lack of signed consent;
- major violations of the protocol;
- incomplete or incorrect data.

14.13.2. Study stopped by the investigator

In the event of an adverse event deemed to be severe by the investigating physician and possibly involving the health of the patients, the latter may stop the study in agreement with the sponsor.

14.13.3. Stopping the study by the patient

Any patient wishing to leave the study for any reason can do so at any time.

In all cases, the investigator should seek to review the patient as soon as possible for a complete final evaluation in order to:

- know the motivation of the decision and mention it on the observation notebook;
- evaluate the clinical condition of the patient;
- if necessary, take the appropriate therapeutic measures: management of a side effect or an intercurrent pathology, prescription of another treatment.

Patients will stop treatment before the end of the study in the case of the occurrence of a serious pathology justifying the prescription of treatments not authorized by the protocol, or incompatible with the continuation of the study, and will come out prematurely of the trial.

The study monitor will be notified by telephone or fax, and a letter or report explaining this study discontinuation will be sent to him as soon as possible.

